In a baseline psychiatric evaluation, study psychiatrists will determine whether (a) medications need to be started, (b) current medications and dosages are appropriate, or (c) current medications need to be adjusted, augmented, or discontinued. Attempts will be made to preserve current regimens; that is, medications will be changed only if necessary, as determined by clinical, psychosocial or academic dysfunction of the child..

Because all study psychiatrists are experienced in the treatment of childhood mood disorders, we will maximize the chances that at-risk or fully syndromal children with BD are appropriately treated. Furthermore, there will be regular monitoring and monthly advisory sessions offered to study psychiatrists when treating complex patients.

During the study, pharmacotherapy can be initiated or modified at any time based on clinical need. If the patient is not taking any medications that would treat his or her condition, then new medications will be instituted, with the goal of decreasing acute symptoms to the point where functioning improves.

Participation in the study will help ensure that the child receives best-practice pharmacotherapy. However, the ultimate choice to start or change medications or dosages will lie with the participating youth and parent(s); no participant will be dropped from the study because of unwillingness to follow the prescribed medication plan.

6.b. Pharmacotherapy Decision Rules

The high-risk and bipolar I/II pharmacotherapy protocols were designed to clarify good clinical practice procedures in these populations. For example, when children have active manic symptoms associated with OSBD or BD I/II, it will usually be necessary to stabilize their mood symptoms before introducing a psychostimulant (Scheffer et al., 2005). Again, there is no requirement that children take any medications in order to be in the study; there are forms of prodromal bipolar disorder that are not severe enough to require medication.

The choice of medications will depend on the patient's current regimen, and his or her current psychiatric state. For example, if the patient has impairing ADHD symptoms and is not taking medications, we will offer to prescribe a psychostimulant or nonstimulant ADD medication and adjust as necessary. If the patient is currently taking an ADHD medication, we will recommend dose adjustments as needed. If the patient has manic symptoms requiring

treatment, we will consider treatment with an atypical antipsychotic, lithium, or another mood stabilizer. If the patient is already taking such a medication, we will recommend dose adjustments as necessary.

Treatment of depressive symptoms is often more complex. Current treatment guidelines suggest that severe depression may need to be treated with an SSRI antidepressant with careful monitoring for the emergence of suicidal behaviors or ideation or mania/hypomania. We recognize that in the population at high-risk for BD, participants are likely to be treated with SSRIs (Chang, 2010) and may be at higher risk of treatment-induced manic or mixed episodes. We will discuss with the family whether to begin treatment with an SSRI, an atypical antidepressant such as bupropion, or other agents used in the treatment of bipolar depression such as lamotrigine or lurasidone. These agents are considered appropriate treatments for children and adolescents with bipolar depression (Kowatch et al., 2005), and their use can be extrapolated to children with depression who are at high-risk for BD ([name] et al., 2017). If an antidepressant is chosen, we will start with a relatively low dose and monitor carefully for any emergence of manic or mixed symptoms.

For those youth who are prescribed medications upon enrollment or are considering starting medications, we suggest the following parameters as a tool to help clinicians, as reflected in the most recent data on high-risk bipolar conditions ([name] et al., 2020):

6.b.1. Prescriber support tool when making pharmacotherapy decisions

Prescribers may choose to begin pharmacotherapy with medications that have evidence from RCTs that support its use (depending on the polarity of the current episode). For example:

- For manic/mixed symptoms: risperidone, olanzapine, aripiprazole, quetiapine, ziprasidone, asenapine, lithium
- For depressive symptoms: lurasidone, quetiapine, lamotrigine, or an antidepressant

The dosing of the medications will be adjusted as clinically necessary and based on clinician's discretion. If the first agent does not lead to symptom resolution, it can be switched to a different agent from the same class or a medication from a different class.

The prescriber will note the rationale for choosing a particular medication on the Physician's Report Form (PRF). If the clinician believes that the medications with evidence for

pediatric bipolar disorder will only be partially effective in a particular patient, other agents (both those with and without FDA regulatory approval) may be considered as add-ons or substitute agents in the current regimen. In every instance, the rationale will be recorded for choice of this agent. The prescriber will also note the dosing of the medication, and the rationale for any deviations from regulatory guidelines.

For patients with comorbid conditions, prescribers will list the psychiatric comorbidities for which they are providing pharmacotherapy. The medications being used and their doses to treat those conditions will be recorded on the PRF. If medications are discontinued, the rationale for this decision will also be recorded by the prescriber.

6.c. Pharmacotherapy Training, Supervision, and Adherence Monitoring

During an initial study launch meeting in year 1 (online or in-person), the study physicians will be trained in the study guidelines for treatment of bipolar I, II, or OSBD patients with or without comorbid conditions. Drug treatment will be monitored throughout the study by the pharmacotherapy oversight committee (Drs. [name], [name], and [name]), who will have monthly conference calls with physicians to discuss complex study cases, decisions to modify treatments, and handle adverse events. Study physicians can receive additional supervision at any other time via teleconference or e-mail.

6.d. Monitoring Adverse Events

Psychiatrists will track any adverse events associated with medications on the Physician's Report Form. The independent evaluators, clinicians, and psychiatrists will record other adverse events (e.g., illnesses, car accidents) on the Adverse Event Form and enter it onto the UCLA REDCAP data capture system. Severe adverse events such as ER visits, hospitalization or suicide attempts, whether study related or not, will be recorded on this form and reported to the local IRB. The Adverse Event Form asks the respondent to describe the event, the likelihood that it is an effect of having a mood disorder, and the probability the event was caused by or related to the study treatments or assessments.

6.e. Psychosocial Treatments

Study psychiatrists and study coordinators will refer patients to appropriate psychosocial interventions as these become available either in the study clinics or in the community. Generally, psychosocial interventions will include psychoeducation and stress management (e.g., mood tracking, development of a relapse prevention plan). In some of the study centers, family interventions may be offered, involving combinations of psychoeducation, communication enhancement training, and problem-solving skills training. Mindfulness therapy groups, cognitive behavioral therapy groups, or dialectical behavior therapy will be offered when available and warranted. The psychoeducational interventions are add-ons to standard care. There are no randomized manipulations of treatments or placebo interventions.

6.f. Study Termination

Study participation will end after the 12-month follow-up. At that point, participants may opt to stay with their study provider (by mutual agreement); if an agreement cannot be reached, the clinician and study staff will provide appropriate referrals for pharmacological and psychological treatment and will continue to treat the participant until such treatment has been arranged. If a new psychiatrist is enlisted, we will send them a treatment report outlining the history of any medication adjustments made during the study. Disclosure of treatment information will require signed HIPAA authorization forms from the parent and child specifying what information will be disclosed and to which doctor.

7. Data Analyses

The data to be collected for this study are based on paper and pencil questionnaires, structured interviews, and pharmacotherapy sessions. Most of the measures have been widely used in studies of childhood mood disorders, including our own studies ([name] et al., 2020). The data will be used only for the purposes of research.

Data used as part of this study will be stored primarily on a shared networking server provided by the UCLA Semel Institute. The network server is located in a locked server room and cabinet and complies with UCLA Health data security protocols and is approved for storage of protected health information. The Semel IT administrators perform regular and encrypted backups of the data. The server is protected using standard security practices including being located behind the UCLA firewall, accessible only by designated users from our staff located at UCLA or

connected through the UCLA VPN from an offsite location. Data transferred using devices (such as USB drives and laptops) will be encrypted following UCLA Health device encryption policies. Storage and access procedures are in full compliance with UCLA Health data security policies.

Our primary analytical techniques will be generalized linear mixed models (GLMMs) and survival analyses, run on an intent-to-treat basis. GLMMs estimate a slope and intercept for each individual and can handle missing data on key outcome variables. Our primary outcomes are symptom severity (i.e., the 1-6 ALIFE Psychiatric Status Ratings) and secondary are remission or recurrence (also recorded on the A-LIFE). The GLMM and survival models will be fit initially without covariates, following standard practices (Kraemer, 2015). We will use logistic regression to identify factors associated with attrition and data loss, and control for these factors in sensitivity analyses. We will protect against multiple comparisons by focusing on a limited set of a priori primary outcomes and contrasts and by reporting results within each hypothesis using false discovery rate procedures (Hochberg & Benjamini, 1990).

For example, when examining the association between study sites and study outcomes, we will code site as a between-subjects variable, symptoms (for example, ALIFE Psychiatric Status Ratings of depression) as the dependent variable, and study visit (baseline, 6 months, or 12 months) as the repeated time variable. These models will examine site by time interactions. There will be subject level random effects to account for individual variation in response trajectories. Covariates may include the child's sex, diagnostic status (bipolar I, II or OSBD), race, ethnicity, or socioeconomic status.

Secondary analyses will concern repeated dependent variables (e.g., parent POWERS ratings) computed from all relevant information at each time point, including information gathered through the MyCoachConnect mobile app. We will determine the degree to which inflammatory variables are associated with changes in symptom severity over 12 months. The correlations between data collected through MyCoachConnect and data collected through interviews and questionnaires will be examined using mixed effect regression models. Using all available variables, we will compute a clinical forecasting model consisting of inflammatory variables at baseline as predictors of symptoms at 0, 6, and 12 months.

7.a. Data Management, Programming Support and Statistical Consulting Services

Management of study data will be accomplished through the REDCAP system. REDCap is a secure, HIPAA-compliant online database that consists of password protected accounts. Demographic, psychiatric, and behavioral data will be stored in REDCap. Prior to analyses, the data will be exported from REDCap into another program such as Excel or R. The data will be immediately stripped of any identifiers (e.g., email, IP address) and the deidentified data will be stored on the UCLA server behind the School of Medicine firewall. All incoming data are purposely filtered, sanitized, and escaped.

REDCap also maintains a built-in audit trail that logs all user activity and pages viewed by every user, including contextual information (e.g., the project or record being accessed), data entry, data export, modifying a field, running a report, or adding/modifying a user. The built-in audit trail in REDCap allows administrators to be able to determine all the activity and all the data viewed or modified by any given user. The REDCap administrator is also available to assist with technical support on research projects. All requests for analysis of datasets must be approved by the PI and site PIs before they are accessed from REDCap.

The UCLA servers are located on the UCLA network behind the School of Medicine (Mednet) firewall and linked to the web server via an internal IP connection. All the servers have 256-bit SSL to provide security for transmission of any sensitive or confidential data and are backed up both locally (incrementally on a daily basis and the full system monthly) and off site (with an encrypted copy of the monthly full back-up image sent to AWS S3 storage.) In addition to the regular IT back-up, there is a secondary full daily back-up for programming code on the web server. The networking server features an hierarchical system of password protected logins.

Study personnel (e.g., [name] at UCLA) will perform ongoing quality checks of the database, monitor the data correction process, and assist study staff with all aspects of system usage and other programming and IT needs. They will coordinate with the site project coordinators and independent evaluators (responsible for entry of paper/pencil forms) to coordinate the timely completion of data deliverables.

Data storage and access procedures will be in full compliance with UCLA Health data security policies. Data transferred using devices (such as USB drives and laptops) will be encrypted following UCLA Health device encryption policies. The default mechanism for electronically transferring files from the sites to UCLA, or from UCLA to individual sites includes either sending through encrypted connections (e.g., SSL/SSH/VPN) and/or encrypting files (256-bit AES

approved using software that supports .zip format, e.g. WinZip) into a single archive, in compliance with UCLA Health data security policies.

7.b. Analysis of Inflammatory Markers

We will examine whether inflammatory markers (C-reactive protein and cytokines such as IL-6 and IL-10) at baseline as a predictors of the symptomatic course of illness over 1 year. At UCLA, blood draws will be done by nurses from the Clinical Treatment Research Center (CTRC) and shipped to the Center for Pathology Services for analysis of inflammatory markers. First, whole blood samples are collected in EDTA tubes. After collection, the samples are centrifuged at 4°C, and plasma harvested into multiple aliquots, and then stored in a -70°C freezer until assayed. Plasma concentrations of inflammatory cytokines are measured in duplicate. Using a Bio-Plex 200 (Luminex) Instrument, Bio-Plex software v4.1, and a 5-parameter logistic curve fit, plasma levels of each cytokine are quantified by means of high sensitivity bead-based multiplex immunoassays (Performance High Sensitivity Human Cytokine, R& D Systems, Minneapolis, MN). All multiplex assays are performed on plasma samples diluted 2-fold according to the manufacturer's protocol, and all calculated concentrations ≥ 0.1 pg/mL generated by the BioPlex Manager software are included in data analyses. All observations deemed undetectable are assigned a value equal to one-half of the plate-specific lower limit and retained in the analysis.

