**The Child Bipolar Disorder Network (CBN): A Collaborative Treatment Study of Youth
With or at High Risk for Bipolar Disorder
V 1.0, March 1, 2022**

(1) Project Summary

The **Childhood Bipolar Network** (CBN) is a recently congregated consortium of 5 universities, all of whom have expertise in diagnosing, assessing and treating bipolar spectrum disorders (BSDs) in children and adolescents. BSD refers to bipolar disorder types I (with full manic episodes), II (major depressions alternating with hypomanic periods), or “otherwise specified” (variations between major depression and subthreshold manic episodes). With one year of funding from the Milken Foundation/Basuzcki Brain Research Fund, we aim to show that the CBN is able to conduct a naturalistic study of youth with BSDs, with assessments and treatment according to a good practice protocol.

We intend to run the CBN over several years, but the objectives of the first year are to conduct a naturalistic treatment and follow-up study across four sites in the US (UCLA, Univ of Pittsburgh Medical Center or UPMC; Virginia Commonwealth Univ (VCU), and University of Colorado Anschutz Medical Campus (UC-AMC)) with the objective of expanding to sites outside of the US. The network will follow a cohort of up to 80 youth with BSDs for up to 12 months, using harmonized methods of assessment and treatment. The protocol will include standardized diagnostic interviews and rating instruments; a pharmacotherapy decision tool, with guidelines to help physicians on what medications to prescribe for what clinical presentations; and a follow-up assessment protocol, including telehealth interviews and rating scales and an online parent-rated instrument called the Parents’ Online Weekly Evaluation and Rating Scales (POWERS) ([name] et al., 2017).

(2) Specific Aims

The aims of the first year of this network are to (1) identify and reliably diagnosis youth (ages 9 yrs to 19 yrs) with BD I, II or otherwise specified BD (OSBD, formerly called bipolar disorder

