not otherwise specified) across collaborative clinics in the US and Canada; and (2) examine predictors of treatment response in up to 80 youth (up to 20/site) with bipolar spectrum disorders (BD I, II or OSBD) followed over 12 months, using harmonized treatment methods and instrumentation. We will measure mood instability (rapid fluctuations in moods, even when youth are not in an illness episode) and an inflammatory marker based on a blood test (C-reactive protein) as predictors of outcome. Accomplishing these objectives will set up the infrastructure for open trials of novel treatments for youth at high-risk for BD spectrum disorders.

Year 1 has several milestones by which progress can be measured: protocol development, IRB approval, cross-site harmonization of assessment and treatment methods, validation of a mood instability phenotype, and development of an open trial infrastructure for novel treatments. Developing standardized procedures across study centers (and eventually, nations) is a critical component of developing treatment algorithms for use in a wide variety of health settings, with culturally heterogeneous populations of youth with or at risk for BSDs.

(3) Background and Significance

Cross-site networks have led to huge advances in the treatment of childhood diseases. Notably, the development of a pediatric cancer network has led to significant reductions in childhood mortality: doctors are now able to focus on dose optimization for individual patients rather than searching for new drugs to treat heterogeneous populations. Similar advances could come from a multi-center network devoted to understanding and treating pediatric bipolar illness. The timing for developing a collaborative bipolar network (CBN) is right because of advances in the reliable diagnosis of *syndromal BD* (types I or II) in children and adolescents and the identification and early treatment of youth at *high risk for BD*. Much of this work has been done at the member sites. Notably, investigators at University of Pittsburgh Medical Center (UPMC), VCU, UCLA, Colorado and collaborators have developed operational criteria for other specified bipolar disorder (OSBD), which presents in youth as brief and recurrent subthreshold periods of mania or hypomania. OSBD is a neglected bipolar subtype that is genetically and clinically very similar to BD I and II, but can be associated with psychosocial impairment that exceeds BD I and II

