At the VCU site participants will be recruited at the Virginia Treatment Center for Children (VTCC). The VTCC has a wing specifically designated for clinical research with interview rooms, laboratory space for blood draws, exam room. This space is located in the same building with outpatient and inpatient psychiatric services.

Participants at the University of Pittsburgh will be recruited and followed at the Child and Adolescent Bipolar Spectrum Services (CABS) clinic. The program is part of Western Psychiatric Hospital of UPMC. The offices are equipped with all of the necessary computing software and hardware to complete the proposed research. Assessments for the proposed study will occur in private offices, either in person or virtually through a HIPAA compliant platform. If a psychiatric emergency should arise, the site PIs are well-trained to assess the need for higher level of care, and refer to appropriate treatment (e.g., emergency room, intensive outpatient program, etc.).

Participants at the University of Colorado Anschutz Medical Campus will be recruited from the Johnson Depression Center (a clinic serving children/adolescents up to adults) as well as the Summit Child Clinic (a general psychiatric clinic that has a child sub-clinic). The offices are equipped with all of the necessary computing software and hardware to complete the proposed research. Assessments for the proposed study will occur in private offices, either in person or virtually through a HIPAA compliant platform. If a psychiatric emergency should

arise, the site PIs are well-trained to assess the need for higher level of care, and refer to appropriate treatment (e.g., emergency room, intensive outpatient program, etc.).

We propose to recruit, diagnose, treat and follow 20 subjects at UCLA and at each of the collaborative sites, for a total of 80 subjects followed for up to one year. In light of recent research collaborations, several of the sites have already established infrastructures for conducting longitudinal and treatment studies of BD or high risk for BD in youth, and collectively, have adequate case flow to achieve the expected sample sizes. Based on our prior experiences, we expect that referrals will be of one of two types: (1) parents who have bipolar disorder who want to have their children evaluated for the disorder; (2) referrals of children with established BD, major depression, hypomania, or significant mood cycling that may meet our eligibility criteria.

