It is likely that we will have study attrition (i.e., participants who agree to the study but, upon evaluation are found not to meet the diagnostic criteria; participants who move away before the study is completed or who leave the study for other reasons). Based on our past studies we are estimating that 80% of participants who sign the initial consent and assent forms will complete the 12-month study. Thus, we will need to recruit 25 participants/site to have a complete sample of 20/site.

On a monthly basis, a Network Oversight Committee consisting of the site PIs and consultants will review proposed participants that present diagnostic complexities, and decide whether the individual meets eligibility criteria for the study. Case information (i.e., results of the Kiddie Schedule for Affective Disorders and Schizophrenia diagnostic interview) will be presented by the diagnostic assessor from the relevant site at these teleconferences, but no PHI will accompany this presentation (i.e., no names or other identifying information).

The Network Oversight Committee will also offer advice to the treating psychiatrist on appropriate medications, dosing, and adjustments. The treating physician will take these recommendations under consideration but will have the final say, in consultation with the parents and child, as to what treatments will be pursued.

5.d. Study advertising

All sites will place advertisements in local newspapers and on local radio stations, and post flyers online, on campus billboards and in selected community health clinics. Physicians, psychiatrists,

and social workers/clinic workers who have previously referred to the program will be made aware of this new study. Regular talks or workshops by study staff at community mental health clinics, primary care clinics, and churches or temples have generated referrals in the past.

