UCLA has an established infrastructure for recruiting children into randomized trials, with UCLA ACCESS, which refers youths to specialty clinics and studies. Additionally, the Child and Adolescent Mood Disorders Program (CHAMP; www.semel.ucla.edu/champ) has a community presence, with a 10-year history of diagnosing and treating bipolar spectrum children and teens. The CHAMP Clinic, which has a staff of five licensed psychologists and three psychiatrists, assesses 2-3 new children or teens each week and verifies all diagnoses with structured diagnostic interviews. Referrals to the clinic have been generated by advertisements and community lectures given by Drs. [name] and other staff members.

At the VCU site participants will be recruited through advertisements in the community, pediatrician offices, as well as clinicians' referrals from the outpatient clinic at the Virginia Treatment Center for Children. The VTCC outpatient clinic serves over 3,000 patients per year, resulting in over 14,000 visits. Additionally, children and their families that are currently participating in other research trials at the VTCC will be offered an opportunity to participate in this study. All referrals will be sent to the study coordinator.

The University of Pittsburgh offers several mediums for participant recruitment which include the CTSI Research Participant Registry/Pitt+Me, the CTSI Pediatric PittNet Network, and several outpatient clinics at Western Psychiatric Hospital, including the Child and Adolescent Bipolar Services (CABS) clinic.

As indicated above, participants at the University of Colorado Anschutz Medical Campus will be recruited from the Johnson Depression Center and the Summit Child Clinic, as well as through advertising and private referral.

5.e. Diagnoses

Kiddie Schedule for Affective Disorders and Schizophrenia, Present and Lifetime Version (KSADS-PL; Kaufman et al., 2013, 2016). The KSADS-PL is a standardized, semi-structured diagnostic interview. Once the parents and youth have signed the consent and assent forms (see Consenting Procedures), a research clinician will administer the KSADS Depression

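### Does Section 5.c of the protocol set two conflicting recruitment targets, 20 and 25 per site?

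*Protocol*

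**What the plan says.** Four places in the protocol bear on the numbers.

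- Section 5.c, Recruitment, sets the aim: "We propose to recruit, diagnose, treat and follow 20 subjects at UCLA and at each of the collaborative sites". The overall figure given there is 80, with at most a year of follow-up.
- The next paragraph of 5.c deals with attrition. It counts two kinds of loss: youth who consent but prove diagnostically ineligible, and "participants who move away before the study is completed or who leave the study for other reasons". It expects that "80% of participants who sign the initial consent and assent forms will complete the 12-month study" and concludes: "Thus, we will need to recruit 25 participants/site to have a complete sample of 20/site".
- Section (1), Project Summary, says: "The network will follow a cohort of up to 80 youth with BSDs for up to 12 months".
- Section (2), Specific Aims, has Aim 2 examine predictors of treatment response in at most 80 youth, at most 20 per site, followed over 12 months.

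Section 5.e places the diagnostic interview after consent ("Once the parents and youth have signed the consent and assent forms"). The 80% completion rate is therefore taken on everyone who consents, including those later found ineligible. Section 7 analyses on an intent-to-treat basis with mixed models that can handle missing outcome data.

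**The concern.** Adjacent paragraphs use the same verb for 20 and for 25 per site, and the implied total of 100 is never printed. The only total a reader meets is 80. A site that took 20 as its recruitment quota would, at the protocol's own completion rate, fall short of the complete sample that the next paragraph asks for.

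There is a second strand. The Project Summary and Aim 2 put a ceiling of 80 on the youth followed, whereas the attrition paragraph makes 80 the number left at the end. A youth who enters follow-up and then leaves has still been followed for a time. If 80 complete, each such youth would push the followed cohort past the ceiling. At stake would be the number of minors asked to consent and a clear statement of the cohort size.

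**Working it through.** **Inputs**

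- Complete sample: 20 per site (Section 5.c, attrition paragraph).
- Completion among those who sign consent: 80% (same paragraph).
- Sites: 4 (Project Summary).
- Total: 80 (Section 5.c, recruitment paragraph).

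**1. The plan's own figure.** Number to recruit = complete sample / completion rate = 20/0.80 = 25 per site. This reproduces the stated 25. The common mistake of adding 20% to the target gives 20 × 1.20 = 24, so the protocol used the right formula.

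**2. Totals.** 4 × 25 = 100 consented, and 100 × 0.80 = 80 completing. The 80 of the recruitment paragraph is thus the number that the attrition paragraph aims to have at the end. The two paragraphs are a target and its inflation for loss, in the usual order.

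**3. The literal alternative.** If 20 per site were the number consented, 20 × 0.80 = 16 per site would complete, or 4 × 16 = 64. That is 4 per site, or 16 in total, below the complete sample. Nothing in the protocol plans for or mentions 64. The figure appears only if the attrition paragraph is ignored.

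**4. The ceiling on youth followed.** Expected losses are 100 − 80 = 20, or 5 per site. Let L be the losses who had already entered follow-up, with 0 ≤ L ≤ 20. The number ever followed is then 80 + L.

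| Assumed split of the 20 losses | L | Ever followed | Excess over 80 |
|---|---|---|---|
| All found ineligible after consent | 0 | 80 | 0/80 = 0% |
| Half and half | 10 | 90 | 10/80 = 12.5% |
| All leave after entering follow-up | 20 | 100 | 20/80 = 25% |

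The protocol does not give the split, so the excess can only be bounded, and the lower bound is zero. The upper bound requires that no youth fails the diagnostic evaluation, although 5.c names that loss first.

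**5. What depends on the number.** No power, precision or interim rule in the protocol uses 80 or 100. The analyses in Section 7 take whoever is enrolled.

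**The case for a change.** The best case for a change is that sites recruit from the protocol, which prints two numbers under one verb, and that a statistical analysis plan would not settle the matter. The limit of up to 12 months in the Project Summary and in 5.c also fits completers poorly, because it takes in youth who leave early, and an upper limit is not the same thing as an expected number remaining.

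The first part stands as a remark on wording: the recruitment paragraph is loosely phrased. It does not stand as a conflict of targets. That paragraph lists four steps (recruit, diagnose, treat, follow) and can fairly be read as the number who pass through all of them. The paragraph after it gives the explicit instruction and the reason for it.

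The second part is a matter of reading. Neither the Project Summary nor Aim 2 states a recruitment figure, and following youth over 12 months, as Aim 2 has it, can mean the full period. Payment for assessments completed before leaving (Section 8) does not show who belongs to the 80, since youth found ineligible after consent may also have completed intake assessments. The intent-to-treat basis names an analysis set and fixes no cohort size.

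The obvious repair would also do harm. Labelling the 80 in Aim 2 as completers would make that aim read as a completer analysis, against the intent-to-treat basis of Section 7.

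**Conclusion.** The inconsistency is real as wording and empty in effect. Recruiting 25 per site as 5.c instructs gives the intended 20 per site, on the protocol's assumption of 80% completion among those who consent. The difference of 5 per site (20 in total) is between a target and its correctly inflated recruitment number. Rewording would add no participants, visits or analyses beyond those that 5.c already implies, and would alter no result.

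The possible excess of 0% to 25% over the ceiling of 80 rests on an unstated split of losses and on one reading of what it means to be followed. It does not show a contradiction. The conclusion assumes that sites read both paragraphs of 5.c and that no sample-size justification elsewhere depends on 80 as the number consented; the protocol contains none. No change to the plan is called for.
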